## 7.2. Subject Discontinuation/Withdrawal from the Study

Reasons for removal of a subject from the study are:

- termination of study by sponsor
- death
- withdrawal of consent from study
- lost to follow-up.

Withdrawal of consent from study:

- A subject may withdraw from the study at any time without jeopardizing subsequent medical care.
- At the time of discontinuing from the study, if possible, an early discontinuation visit should be conducted, as shown in the SoA. See SoA ([Section 1.3](#)) for data to be collected at the time of study discontinuation and follow-up and for any further evaluations that need to be completed.
- The subject will be permanently discontinued from the study drug and the study at that time.
- If the subject withdraws consent for disclosure of future information, the sponsor may retain and continue to use any data collected before such a withdrawal of consent.
- If a subject withdraws from the study, he/she may request destruction of any samples taken and not tested, and the investigator must document this in the site study records and notify the sponsor or its designee.

### **7.3. Lost to Follow-up**

A subject will be considered lost to follow-up if the subject repeatedly fails to return for scheduled visits and is unable to be contacted by the site.

The following actions must be taken if a subject fails to return to the clinic for a required study visit:

- The site must attempt to contact the subject and reschedule the missed visit as soon as possible, counsel the subject on the importance of maintaining the assigned visit schedule and ascertain whether the subject wishes to and/or should continue in the study.
- Before a subject is deemed lost to follow-up, the investigator or designee must make every effort to regain contact with the subject (where possible, [3] telephone calls, and if necessary, a certified letter to the subject's last known mailing address or local equivalent methods). These contact attempts should be documented in the subject's medical record.
- Where permitted by local regulations and approved by IRBs/IECs, third-party vendors may be employed by the site (funded by the sponsor) to assist the site in re-establishing contact.

## 8. Study Assessments and Procedures

- Informed consent must be obtained before any study-related procedures are performed. In regions where the legal age of consent is older than 18 years, informed consent must be obtained from and signed by the subject.
- Study procedures and their timing are summarized in the SoA ([Section 1.3](#)). Protocol waivers or exemptions are not allowed.
- Day 1 corresponds to the date of the first dose of study drug.
- Visit/dosing windows of  $\pm$  3 days on either side of the scheduled visits/dosing are permitted; however, the investigator should try to keep the subjects on the original visit/dosing schedule. The window of  $\pm$  3 days is relative to Day 1 and applicable for all subsequent visits/dosing. The time between doses should be no less than 4 days and no more than 13 days.
- All assessments are to be completed before study drug administration, unless otherwise specified. It is recommended that patient-reported outcome assessments be completed first.
- Immediate safety concerns should be discussed with the sponsor immediately upon occurrence or awareness to determine if the subject should continue or discontinue study drug.
- Adherence to the study design requirements, including those specified in the SoA, is essential and required for study conduct.
- All screening evaluations must be completed and reviewed to confirm that potential subjects meet all eligibility criteria. The investigator will maintain a screening log to record details of all subjects screened and to confirm eligibility or record reasons for screening failure, as applicable.
- Procedures conducted as part of the subject's routine clinical management (eg, x-rays) and obtained before signing of the ICF may be utilized for screening or baseline purposes provided the procedures met the protocol-specified criteria and were performed within the timeframe defined in the SoA.
- Repeat or unscheduled samples may be taken for safety reasons or for technical issues with the samples.

### 8.1. Efficacy Assessments

Planned timepoints for all efficacy and/or immunogenicity assessments are provided in the SoA. The site should make every attempt to have the same investigator conduct efficacy assessments throughout the study for each subject.

#### 8.1.1. Hidradenitis Suppurativa Clinical Response

The HiSCR was developed to address issues with available HS scoring systems and is a validated measure that is responsive to improvement in disease activity, simplifies the scoring process, and increases the sensitivity to detect HS-specific lesions (Kimball et al, 2014; Kimball et al, 2016). The HiSCR50 is defined as at least a 50% reduction from baseline in the total AN count, with no increase from baseline in abscess or draining fistula count. HiSCR75,

HiSCR90, and HiSCR100 are defined as at least 75%, 90% or 100% reduction respectively from baseline in the total AN count, with no increase from baseline in abscess or draining fistula count.

#### **8.1.2. Lesion and AN Count**

The number of inflammatory and non-inflammatory nodules, abscesses, draining and nondraining fistulas, and hypertrophic scars, as well as the physical location (eg, right/left axilla, right/left inframammary, intermammary, right/left buttock, right/left inguino-crural fold, perianal, perineal, other) will be recorded at the designated study visits listed in SoA ([Section 1.3](#)). The AN count is the sum of abscesses and inflammatory nodules. In addition, lesions counts will be performed at any time if the subject experiences a disease flare. The longest distance between 2 relevant lesions (if only 1 lesion, measure diameter of lesion) and whether the lesions are clearly separated by normal-appearing skin (yes or no) will be measured. The calculation of the HiSCR, International Hidradenitis Suppurativa Severity Score System (IHS4), and modified Sartorius score will be performed by the sponsor or designee based on the lesion counts entered by the study investigator(s) on the appropriate CRFs. In addition, the sponsor or designee will utilize the lesions counts entered by the investigator on the CRF to establish the rate of flares.

Treatment decisions made during the conduct of the study will not be based on the HiSCR.

#### **8.1.3. Hurley Stage**

The Hurley Stage is a severity classification for HS that was developed in 1989 and is widely used for the determination of the severity of HS (Hurley, 1989). The Hurley Stage is defined by the following criteria:

- Stage I: Abscess formation, single or multiple, without sinus tracts and cicatrization (scarring).
- Stage II: Recurrent abscesses with tract formation and cicatrization, single or multiple, widely separated lesions.
- Stage III: Diffuse or near-diffuse involvement, or multiple interconnected tracts and abscesses across the entire area.

The study investigator will determine the Hurley Stage in each affected anatomical region at the designated study visits listed in the SoA ([Section 1.3](#)). If more than 1 stage is present in a region, the worst state in each region should be entered.

#### **8.1.4. Numeric Rating Scale Patient Global Assessment of Skin Pain**

The NRS Patient Global Assessment of Skin Pain will be completed on a daily diary by subjects from screening through Week 16, and at the designated study visits after Week 16, listed in SoA ([Section 1.3](#)). If pain diaries are not completed for at least 3 of the 7 consecutive days prior to the Day 1 visit, the subject may not be randomized.

The Patient Global Assessment of Skin Pain is a unidimensional NRS that allows for rapid (often 1 item) measures of pain that can be administered multiple times with minimal administrative burden. The NRS consists of scores from 0 to 10 with 0 indicating “no skin pain” and 10

indicating “pain as bad as you can imagine”. The pain will be described as “skin pain at its worst in the last 24 hours” and “skin pain on average in the last 24 hours”.

The subject should complete the questionnaire before site personnel perform any clinic assessments and before any interaction with the site personnel has occurred to avoid biasing the subject’s response.

#### **8.1.5. Dermatology Life Quality Index**

Subjects will complete the DLQI questionnaire at the designated study visits listed in SoA (Section 1.3). The DLQI will be used to assess the symptoms and the impact of skin problems on quality of life. The DLQI can be used to evaluate 6 areas: symptoms and feelings, daily activities, leisure, work and school, personal relationships, and treatment (Finlay and Khan 1994). Subjects will be asked to respond to the 10 items of the DLQI based on a recall period of “the last week”. Decreased scores indicate improved health-related quality of life. The subject should complete the questionnaire before site personnel perform any clinic assessments and before any interaction with the site personnel has occurred to avoid biasing the subject’s response.

#### **8.1.6. Modified Sartorius Score**

The Sartorius scale was created as a more detailed and dynamic HS severity scale and was modified in order to further develop and simplify this assessment for the clinical setting (Sartorius et al, 2009; Sartorius et al, 2010). The modified Sartorius score was the first disease-specific instrument for dynamically measuring clinical severity. The main parameter in the modified Sartorius score is the counting of individual nodules and fistulas. The modified Sartorius score includes an assessment of the anatomical regions involved, the numbers and scores of lesions for each region, the longest distance between 2 relevant regions (or size of a single lesion), and whether all lesions are separated by normal skin (yes or no).

#### **8.1.7. International Hidradenitis Suppurativa Severity Score System**

The IHS4 is a validated tool to dynamically assess HS severity to be used both in real-life and clinical study setting. The determination of IHS4 requires counting the nodules, abscesses, and draining fistulas/sinus tracts. The IHS4 score (points) = (number of nodules × 1) + (number of abscesses × 2) + (number of draining tunnels [fistulae/sinuses] × 4). A score of  $\leq 3$  signifies mild HS, a score of 4 to 10 signifies moderate HS, and a score of  $\geq 11$  signifies severe (Zouboulis et al, 2017).

#### **8.1.8. Hidradenitis Suppurativa-Physician’s Global Assessment**

The hidradenitis suppurativa-Physician’s Global Assessment (HS-PGA) is a validated 6-point scale that is used to measure improvement in inflammatory nodules, abscesses, and draining fistulas (Kimball et al, 2012; Zouboulis et al, 2015). The HS-PGA scale is defined by the following:

- Clear: No inflammatory or non-inflammatory nodules
- Minimal: Only the presence of non-inflammatory nodules
- Mild:  $< 5$  inflammatory nodules or 1 abscess or draining fistula and no inflammatory nodules

- Moderate:  $\geq 5$  inflammatory nodules or 1 abscess or draining fistula and  $\geq 1$  inflammatory nodule or 2 to 5 abscesses or draining fistulas and  $< 10$  inflammatory nodules
- Severe: 2 to 5 abscesses or draining fistulas and  $\geq 10$  or more inflammatory nodules
- Very severe:  $> 5$  abscesses or draining fistulas.

### **8.1.9. European Quality of Life-5 Dimensions**

The European Quality of Life-5 Dimensions (EQ-5D) comprises 5 questions on mobility, self-care, pain, usual activities, and psychological status with 3 possible answers for each item (1 = no problem, 2 = moderate problem, 3 = severe problem). A summary index with a maximum score of 1 can be derived from these 5 dimensions by conversion with a table of scores. The maximum score of 1 indicates the best health state, by contrast with the scores of individual questions, where higher scores indicate more severe or frequent problems. In addition, there is a visual analog scale to indicate the general health status with 100 indicating the best health status.

### **8.1.10. Short Form 12**

The acute Short Form-12v2™ Health Survey (SF-12v2) is a 7-day recall, 12-item subset of the Short Form-36v2™ questionnaire that measures the same 8 domains of health including physical functioning, role-function, bodily pain, general health, vitality, social functioning, role-emotional, and mental health. The SF-12 is a brief, reliable measure of overall health status with scores general for physical component and mental components. Each item on the SF-12 is score on 3- or 5-item Likert scales and the domains scales are standardized to 0 to 100 scale where 0 represents lower quality of life and 100 represents higher quality of life. The subject should complete the questionnaire before site personnel performs any clinic assessments and before any interaction with the site personnel has occurred to avoid biasing the subject's response.

### **8.1.11. Hidradenitis Suppurativa Quality of Life**

Subjects will complete Hidradenitis Suppurativa Quality of Life (HiSQOL) scale at the designated study visits listed in the SoA ([Section 1.3](#)). The 17-item HiSQOL questionnaire includes 4 symptom items, 8 activity-adaptation items, and 5 psychosocial items. The item scores are summed to create a total ranging from 0 to 68, with higher scores indicating a more severe impact on health-related quality of life (Kirby et al, 2020).

### **8.1.12. Hidradenitis Suppurativa Patient Global Impression of Change**

Subjects will complete the HS Patient Global Impression of Change (PGIC) questionnaire at the designated study visits listed in SoA ([Section 1.3](#)). The PGIC consists of 1 self-administered item that assesses change in the severity of skin pain due to HS. Subjects are asked to indicate their impression of change compared with their last visit, except at Week 12 and Week 16, when the subject will also be asked about their pain since treatment began on this study.

### **8.1.13. Hospital Anxiety and Depression Scale**

In addition, depression and anxiety will be monitored with the Hospital Anxiety and Depression Scale (HADS). The HADS was chosen for its well-established psychometric properties and its use in clinical research on biological therapy in subjects with other inflammatory skin diseases

(Langley et al, 2010). The HADS scores for anxiety and for depression range from 0 to 21 with higher scores indicating a worse state. A score  $< 8$  is considered to be normal, whereas a score of  $\geq 11$  is considered clinically significant (Snaith, 2003).

The HADS questionnaire will be presented in local language and is to be completed by the subject at the designated study visits listed in the SoA ([Section 1.3](#)).

#### **8.1.14. Photography (Optional Substudy)**

Subjects at a subset of selected sites will be invited to participate in an optional substudy to have photographs taken of their disease response during the study. Subjects who consent to this optional substudy will have photographs taken at the designated study visits listed in the SoA ([Section 1.3](#)). Sites participating in the photography substudy will be trained and receive standardized photographic equipment from the central photography vendor. Sites will submit the digital images to the central photography vendor. Photographs will be anonymized.

### **8.2. Safety Assessments**

Planned timepoints for all safety assessments are provided in the SoA ([Section 1.3](#)).

#### **8.2.1. Medical and Medication History**

A complete medical and medication history, as well as a history of alcohol and nicotine use, will be obtained from each subject during the screening visit. An updated medical history will be obtained at the Day 1 visit prior to study drug administration and updated as necessary throughout the study.

A HS history obtained at screening will capture date of onset of HS.

Any systemic treatment for HS since diagnosis will be recorded. Any other treatment used for any other reasons (including contraception) prior to randomization will be recorded as per eCRF Completion Guidelines.

Any changes in concomitant medication will be recorded throughout the study, from Day 1 until end of study at Week 59.

#### **8.2.2. Physical Examinations**

A complete physical examination will include, at a minimum, assessments of the dermatological, cardiovascular, respiratory, gastrointestinal, and neurological systems.

Clinically significant findings observed prior to the first dose of study drug should be listed as medical history in the CRF and reported as AEs if observed after first dose of study drug.

#### **8.2.3. Vital Signs**

Vital signs will be measured in a sitting position after 5 minutes rest and will include temperature, systolic and diastolic blood pressure, pulse, and respiratory rate.

#### **8.2.4. Physical Measurements**

Height and weight measurements are to be performed at the timepoints indicated in the SoA and data will be recorded in centimeters and kilograms respectively. Height and weight are to be measured without shoes.

#### **8.2.5. Electrocardiograms**

TriPLICATE 12-lead ECGs will be obtained after subject has been supine for at least 5 minutes as outlined in the SoA ([Section 1.3](#)) using an ECG machine that automatically calculates the heart rate and measures PR, QRS, and QT intervals.

#### **8.2.6. Chest X-ray**

Only subjects with a positive or indeterminate IGRA TB test will undergo a chest x-ray (posterior/anterior or anterior/posterior). A subject must not be included in the study if his/her chest x-ray reveals evidence of active TB (refer to [Section 5.1](#)). Women of childbearing potential must have a negative pregnancy test before an x-ray is performed.

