Study drug dispensation and dosing a, n, o		X p	X p	X	X	X	X	X	X p	X p	X	X	X	X			
Dosing diary q								←			→						

Footnotes are defined on the next page.

ADA = anti-drug antibody; AE = adverse event; AN = abscess and inflammatory nodule; CRF = case report form; C-SSRS = Columbia-Suicide Severity Rating Scale; d = day; DLQI = Dermatology Life Quality Index; ECG = electrocardiogram; EOS = end of study; EOT = end of treatment; EQ-5D = European Quality of Life 5-dimension; ET = early termination; HADS = Hospital Anxiety and Depression Scale; HBV = Hepatitis B virus; HCV = Hepatitis C virus; HiSQOL = Hidradenitis Suppurativa Quality of Life; HIV = human immunodeficiency virus; HS-PGA = Hidradenitis Suppurativa-Physician's Global Assessment; HS-PGIC = Hidradenitis Suppurativa Patient Global Impression of Change; IGRA = interferon-gamma release assay; NRS = Numeric Rating Scale; PK = pharmacokinetic; SAE = serious adverse event; SF-12 = 12-Item Short Form Survey; TB = tuberculosis; US = United States; WOCBP = women of childbearing potential.

a Visit/dosing windows of  $\pm$  3 days on either side of the scheduled visits/dosing are permitted; however, the investigator should try to keep the subjects on the original visit/dosing schedule. In case of a delayed or missed dose, the investigator should return subjects on the original visit/dosing schedule in relation to Day 1 for subsequent doses. The window of  $\pm$  3 days is relative to Day 1 and applicable for all subsequent visits/dosing. The time between doses should be no less than 4 days and no more than 13 days.

b The EOT visit will be completed at Week 52 ( $\pm$  5 days) and safety follow-up visit completed at Week 59 ( $\pm$  5 days). For subjects who early terminate, these visits should be completed 1 week ( $\pm$  5 days) and 8 weeks ( $\pm$  5 days) after the last dose of study drug.

c Vital signs include measurements of temperature, respiratory rate, systolic and diastolic blood pressure, and pulse.

d Chest x-ray (posterior/anterior or anterior/posterior) will be performed at screening only for subjects who do not have a chest x-ray available within 3 months prior to screening. Women of childbearing potential must have a negative pregnancy test before x-ray is performed.

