11. Active infection or history of infection as follows:
  - a. Any active infection for which oral anti-infectives (antibiotics, antivirals, antifungals) were used  $\leq$  14 days prior to first dose of study drug (except for the use of a stable dose allowable antibiotics [doxycycline or minocycline only] for HS).
  - b. A serious infection requiring hospitalization or IV anti-infectives (antibiotics, antivirals, antifungals)  $\leq$  30 days prior to first dose of study drug.
  - c. Recurrent or chronic infections or other active infections that in the opinion of the investigator might cause this study to be detrimental to the subject.
12. *Candida* infection requiring systemic treatment within 3 months prior to first dose of study drug.
13. Tuberculosis or fungal infection seen on available chest x-ray taken within 3 months prior to screening (Exception: documented evidence of completed treatment and clinical resolution).
14. Known history of human immunodeficiency virus (HIV) or positive HIV test at screening.

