### **6.3.2. Rescreening**

Investigators may rescreen a subject if the investigator is reasonably certain that reasons for screen failure will be resolved prior to or during a repeat screening attempt. Reasons to rescreen may include but are not limited to the following:

- Laboratory value(s) out of range due to sampling error or that might be within range after medically appropriate supplementation. (Note: Before screen failing and then rescreening the subject, efforts should be made to repeat the laboratory assessment(s) during the original initial screening period.).
- The subject has a medical condition that can be stabilized or resolved prior to the repeat screening/rescreening attempt; or
- Additional time is required following the subject’s last dose of an excluded medication.

Investigators are encouraged to consult with the medical monitor prior to rescreening subjects for other reasons.

A subject must provide informed consent prior to the initiation of any rescreening procedures only if 30 or more days have elapsed since the date of the subject’s initial informed consent. The subject is entered into rescreening in the IXRS, and all screening procedures must be repeated

except as noted in the inclusion/exclusion criteria. A subject may be screened up to 3 times (ie, no more than 2 rescreens). Near to the end of study enrollment, sites may be notified when no additional subjects will be screened or rescreened.

If a subject rescreens, a chest x-ray does not need to be repeated if a previous chest x-ray was performed  $\leq$  3 months prior to Day 1.

If a subject rescreens, hepatitis, TB, HIV, urinalysis, and electrocardiogram (ECG) tests do not need to be repeated if a previous test was performed  $<$  60 days prior to Day 1.

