#### **8.2.8. Tuberculosis Test**

Determination of TB status will be required before the subject's inclusion in the study. An IGRA TB test (QuantiFERON recommended), chest x-ray (unless already performed within 3 months prior to screening), and examination for signs and symptoms of TB will be performed on each

subject to assess TB status at screening. **Table 8-1** provides TB terms and definitions for the purpose of the study, and **Table 8-2** provides guidance for handling various TB test results.

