**Table 8-1. Tuberculosis Terms and Definitions**

Term	Definition
Known TB	
 
• Active TB or presence of symptoms (pulmonary or extra-pulmonary) consistent with TB
 
• History of active TB or findings consistent with TB, unless there is documented evidence of completed treatment and clinical resolution, by a TB specialist
 
• Radiological or other imaging modalities findings consistent with previously active TB that is not reported in the subject's medical history
 

High risk of acquiring TB	
 
• Close contact with a person with active TB within the 3 months prior to screening
 
• Working in or attending a healthcare setting or facility housing persons with TB where there is a high risk of transmission
 

Latent TB	
 
• Positive IGRA TB test (or 2 indeterminate IGRA TB test results) with absence of symptoms (pulmonary or extra-pulmonary) and radiological or other imaging modalities findings consistent with active TB
 
• If available, respiratory or other specimens must also be smear and culture negative for TB (Center for Disease Control diagnosis of latent TB; http://www.cdc.gov/TB/topic/testing/default.htm)
 

Nontuberculous mycobacterial infection	
 
• Clinical manifestation of infection caused by mycobacteria species other than M tuberculosis
 

CDC = Centers for Disease Control and Prevention; IGRA = interferon-gamma release assay; TB = tuberculosis; WHO = World Health Organization

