**Table 8-2. Tuberculosis Testing Results and Required Actions**

Initial IGRA TB Test a Results for Eligibility		
Negative	Indeterminate	Positive
Required action		
No further action is needed, subject is eligible for the study	
Repeat IGRA TB test (must be completed during the protocol-defined screening period)
 
 
• If negative, no further action is needed, subject is eligible for the study
 
• If indeterminate or positive, subject must be referred to a TB specialist for further evaluation 
 
○ If subject is determined to be negative for latent or active TB by the TB specialist, subject is eligible for the study
 
○ If diagnosed with active TB by the TB specialist, subject is NOT eligible for the study
 
○ If diagnosed with latent TB by the TB specialist, eligibility must be discussed with the medical monitor and the subject must complete at least 4 weeks of prophylaxis in accordance with WHO/CDC guidelines prior to first dose of study drug and continue to the full treatment course to completion
 
 
 
	
 
• Subject must be referred to a TB specialist for further evaluation 
 
○ If subject is determined to be negative for latent or active TB by the TB specialist, subject is eligible for the study
 
○ If diagnosed with active TB by the TB specialist, subject is NOT eligible for the study
 
○ If diagnosed with latent TB by the TB specialist, to be eligible for the study, subject must complete at least 4 weeks of prophylaxis in accordance with WHO/CDC guidelines prior to first dose of study drug and continue to the full treatment course to completion
 
 
 

CDC = Centers for Disease Control and Prevention; IGRA = interferon-gamma release assay; TB = tuberculosis; WHO = World Health Organization

aQuantiFERON recommended.

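### Protocol 8.2.6 restricts the screening chest x-ray to IGRA-positive or indeterminate subjects, contradicting Section 8.2.8 and Schedule of Activities footnote d

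*Protocol*

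**What the plan says.** The protocol states the chest x-ray rule in several places.

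- **Section 8.2.6 (Chest X-ray):** "Only subjects with a positive or indeterminate IGRA TB test will undergo a chest x-ray". Its next sentence bars inclusion if the film shows active tuberculosis, so this is the screening film.
- **Section 8.2.8 (Tuberculosis Test):** among the screening procedures, a "chest x-ray (unless already performed within 3 months prior to screening), and examination for signs and symptoms of TB will be performed on each" subject. There is no IGRA condition.
- **Section 1.3, Schedule of Activities, footnote d:** the film "will be performed at screening only for subjects who do not have a chest x-ray available within 3 months prior to screening". Again there is no IGRA condition.
- **Section 6.3.2 (Rescreening):** "If a subject rescreens, a chest x-ray does not need to be repeated if a previous chest x-ray was performed" no more than 3 months before Day 1. The waiver depends on the age of the film.
- **Section 5.2, exclusion criterion 13:** excludes for "Tuberculosis or fungal infection seen on available chest x-ray taken within 3 months prior to screening", with an exception for documented completed treatment and clinical resolution.
- **Table 8-1:** under known TB it lists "Radiological or other imaging modalities findings consistent with previously active TB that is not reported in the" medical history.
- **Table 8-2, negative IGRA column:** "No further action is needed, subject is eligible for the study".
- **Section 8:** "Adherence to the study design requirements, including those specified in the SoA, is essential and required for study conduct". The same section allows no waivers.

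**The concern.** Section 8.2.6 makes the film depend on the IGRA result. Section 8.2.8 and footnote d make it depend only on whether a recent film exists. A coordinator who looks up the section titled Chest X-ray finds a rule that omits the film for IGRA-negative subjects.

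The safety consequence is narrow but real. An IGRA does not test for fungal disease, so without a film nothing radiographic stands behind the fungal part of exclusion 13. The Table 8-1 category of unreported radiological findings of past tuberculosis would also go unchecked. The protocol itself lists tuberculosis and opportunistic, serious or fungal infections as events of special interest (Section 8.3.6), so the check matters for a drug that inhibits IL-17A.

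**Working it through.** No sample size, alpha or power figure is involved, so the check is a comparison of the texts. All of them are current protocol text, not the amendment summary.

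**Step 1. Apply each rule to the four possible screening situations.**

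| IGRA result | Film in prior 3 months? | 8.2.6 | 8.2.8 and footnote d | Agree? |
|---|---|---|---|---|
| Negative | Yes | No x-ray | No new x-ray | Yes |
| Negative | No | No x-ray | X-ray required | **No** |
| Positive or indeterminate | Yes | X-ray, read literally | No new x-ray required | **No** |
| Positive or indeterminate | No | X-ray | X-ray required | Yes |

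The second row carries the safety consequence. The third would at most produce an extra film.

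**Step 2. Can 8.2.6 be read as an addition to a universal film?** No. It opens with the word Only, which excludes that reading.

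**Step 3. Which text is the outlier?**
- Section 8.2.8, footnote d and Section 6.3.2 all work from film age, and none mentions IGRA.
- Exclusion 13 and the known-TB definition in Table 8-1 act on imaging findings regardless of IGRA.
- Section 8 makes the Schedule of Activities binding, so omitting the film in the second row is a deviation.
- Section 8.2.6 refers to Section 5.1 for its criterion, but the TB criteria there (inclusion 9 and 10) contain no x-ray criterion. That criterion is exclusion 13, in Section 5.2.

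Only 8.2.6 ties the film to the IGRA result.

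**Step 4. Would another step recover the missing film?** Table 8-2 would not, because after a negative IGRA it asks for nothing more. Exclusion 13 would not either. It is conditional on an available film from before screening and does not itself require one. Read literally, it also misses a fungal finding on a film taken at screening under footnote d. Active tuberculosis on that film is covered by the second sentence of 8.2.6.

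**Step 5. Size.** Number affected = 250 × (share IGRA-negative with no recent film) × (share of those at sites that follow 8.2.6). The 250 is the planned enrolment (Section 4.1.3). Neither share is given, nor is the number of the approximately 95 sites (Section 4.1.2) that would follow 8.2.6. With both shares between 0 and 1, the result lies between 250 × 0 × 0 = 0 and 250 × 1 × 1 = 250.

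**The case against.** The strongest case on the other side accepts the conflict and argues that it is minor.

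- **A site would have to overlook footnote d, Section 8.2.8 and the Section 8 instruction on the schedule.** That makes omission less likely. It does not remove an explicit contrary rule in the section devoted to the x-ray.
- **IGRA-negative subjects who already have a recent film are still covered by exclusion 13.** Correct. The exposure is limited to those without one.
- **Other criteria catch infection.** Exclusion 11 covers recently treated or serious infection and, at the investigator's discretion, recurrent, chronic or other active infection. Exclusion 10 covers any clinically significant condition judged to pose a risk, and the physical examination includes the respiratory system. This stands. What remains is mainly a clinically silent radiographic finding in an IGRA-negative subject, and discretionary criteria cannot act on a finding nobody has looked for.
- **Table 8-2 only governs handling of IGRA results.** Fair. It does not create the conflict, but it would not alert a site to the missing film.
- **The exclusion 13 wording is a separate and weaker point.** It is secondary, and exclusions 10 and 11 leave the investigator discretion to exclude a fungal finding. The literal gap is still there.
- **Section 6.3.2 counts film age from Day 1, while footnote d and 8.2.8 count from screening.** True. It does not affect the point that none of the three depends on IGRA.
- **Screening is probably over.** The SAP describes the Week 12 primary analysis as done (Section 8.6) and the study as ending early after Week 32 (Sections 2 and 4.1). If so, an amendment would change no subject's screening here. That limits the practical benefit, not the correctness of the finding.

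**Conclusion.** The concern holds. The first sentence of 8.2.6 is wrong as written and would lead a site to omit a safety check that the Schedule of Activities requires. It is an internal contradiction, not a dispute about the intended design, and it should be corrected.

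The extent is unknown and depends on how sites resolved the conflict. The effect is confined to radiographic findings in IGRA-negative subjects without a recent film that the other checks do not catch. The primary endpoint, type I error and power are untouched. The conclusion rests on reading 8.2.6 as the screening film, which its own inclusion rule supports.

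**What to change.** 1. Replace the first sentence of 8.2.6 with a rule to this effect: at screening, every subject without a chest film from the preceding 3 months has one taken (posterior/anterior or anterior/posterior), irrespective of the IGRA result. Leave the rescreening allowance in 6.3.2 in place.
2. Reword exclusion 13 so that it covers tuberculosis or fungal infection on a film taken either at screening or in the 3 months before it, keeping the exception for completed treatment with clinical resolution.
3. If enrolment has closed, identify and document any subjects randomized without a qualifying film, and correct the same sentence in any related protocol that carries it.

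The cost of the first two is a short amendment or clarification letter. The only additional films are for IGRA-negative subjects without a recent one, and the schedule already calls for those. The third is a records check.
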